Refer to Section 7.2.7 for details of laboratory safety sampling and to Section 7.4.2 for details of blood glucose safety sampling.

When the t=90-minute blood sampling for plasma glucose has been collected the subjects are allowed to eat moderately. Drinking of water is allowed *ad libitum* during the entire procedure.

Hypoglycemia Rescue Provisions

During insulin-induced hypoglycemia, plasma glucose levels will be monitored closely at site for safety reasons as described in Section 7.4.2. Subjects should receive post-treatment rescue glucose infusion to ameliorate persistent hypoglycemia, as follows.

1. Glucose infusion should be initiated if a subject experiences severe alarming escalation of symptoms of hypoglycemia (e.g. symptoms suggesting a change in consciousness) at any time during the trial; glucose infusion should be initiated targeting a plasma glucose levels >70 mg/dL.
2. If plasma glucose is <45 mg/dL (2.5 mmol/L) between t=8 and t=44 minutes, rescue glucose infusion (1-2 mg/kg administered IV over about 5 seconds) should be initiated to maintain plasma glucose between 45 mg/dL and 55 mg/dL (2.5-3.1 mmol/L). Pause glucose infusion if plasma glucose is >55 mg/dL.
3. If plasma glucose is <70 mg/dL at t=45 minutes, rescue glucose infusion (2-3 mg/kg administered IV over about 5 seconds) should be initiated to maintain plasma glucose between 70 mg/dL and 80 mg/dL (3.9-4.4 mmol/L). Pause glucose infusion if plasma glucose is >75 mg/dL (4.2 mmol/L).

Subjects should remain in bed until completion of the test procedure 300 minutes after dosing (bathroom visits are allowed).

The IMP will be administered SC according to Section 6.3. The time of IMP administration will be recorded. At the timepoint when the insulin infusion is stopped, the total insulin dose which was required to induce hypoglycemia will be recorded.

AEs will be specifically recorded during the procedure at several timepoints.

The investigator must provide information to the subjects on how to resume their usual diabetes treatment.

The subject may be released from the clinical center if the investigator does not have any safety concerns based on the last safety plasma glucose value and the general condition of the subject. However, at the discretion of the investigator or on request of the subject, the subject may stay at the trial center for a longer period.

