9.5.4 Secondary clinical efficacy (PD) endpoints

- Time to first plasma glucose concentration of ≥ 70 mg/dL (3.9 mmol/L) without administration of rescue IV glucose.
- Plasma glucose response as area under the curve above baseline from time zero to 30 minutes, $AUC_{0-30min}$.

Secondary clinical efficacy endpoints will be assessed based on plasma concentration data from samples collected at the dosing visit (Visit 2).

Unless otherwise stated, the population base of analysis will be the FAS.

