9.5.4.1 Analysis of secondary clinical efficacy (PD) endpoints

1. Time to first plasma glucose concentration ≥ 70 mg/dL from baseline. This time-to-event endpoint will be evaluated using a Kaplan-Meier approach, with treatment group as a stratification factor, analogous to that used for the primary endpoint analysis. Differences between the KM curves (dasiglucagon versus placebo, GlucaGen versus placebo) will be evaluated inferentially using pairwise two-sided log rank tests. If the ≥ 70 mg/dL endpoint is not met within 45 minutes post-dosing, the time of the last valid plasma glucose measurement up to 45 minutes will be the censoring time.
2. The AUC will be calculated as the baseline-adjusted area under the plasma glucose profile over time:
 - a. $AUC_{0-30min}$: restricting the time window to the 0 to 30 minutes interval.
3. The log-transformed AUC endpoint will be analyzed using an analysis of covariance (ANCOVA) model with treatment as fixed effect and baseline plasma glucose modeled as a covariate. The least squares means treatment group differences will be back-transformed (anti-logged) for presentation as a ratio of the treatment group geometric means, with their corresponding 95% CI.

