9.9 Subject withdrawals and missing data

In the case of subject withdrawal, no imputation of values for PK or PD measurements will be done. Analyses will be done on valid cases only, i.e., no imputation techniques such as last observation carried forward will be applied. For the primary analysis in the FAS, missing values for the primary endpoint will be imputed by a conservative rule considering any missing value as a failure.

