The continuous clinical efficacy variables, the exploratory variables, and the pharmacokinetics variables will each be summarized descriptively by treatment group. The clinical efficacy variables will be analyzed analogous to the plasma glucose CFB variables.

The safety analyses will include by-treatment-group descriptive summaries of vital sign measurements, laboratory measures (including immunogenicity incidence), physical examination assessments, rescue IV glucose (incidence and amount of glucose infused), and adverse events. The number and percentage of subjects reporting specific events, such as nausea and vomiting, will be presented by body system and preferred term.

Further details will be included in the Statistical Analysis Plan, to be completed before database lock and treatment unmasking.

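### The log-transformed, baseline-adjusted glucose AUC0-30min is undefined for subjects whose glucose does not rise, and the protocol gives no rule for them

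*Protocol*

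**What the plan says.** Section 9.5.4 defines the endpoint as "Plasma glucose response as area under the curve above baseline from time zero to 30 minutes". Section 9.5.4.1 derives it thus: "The AUC will be calculated as the baseline-adjusted area under the plasma glucose profile over time". It then fixes the model: "The log-transformed AUC endpoint will be analyzed using an analysis of covariance (ANCOVA) model with treatment as fixed effect", with baseline plasma glucose as covariate. Treatment differences are to be "back-transformed (anti-logged) for presentation as a ratio of the treatment group geometric means". No offset, floor or other rule for values at or below zero is stated. These items read the same in each version of the protocol in the file.

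On the population, section 9.5.4 says: "Unless otherwise stated, the population base of analysis will be the FAS". On missing data, section 9.9 says: "Analyses will be done on valid cases only, i.e., no imputation techniques such as last observation carried forward will be applied". The synopsis describes the same analyses more loosely: "The clinical efficacy variables will be analyzed analogous to the plasma glucose CFB variables". The change-from-baseline (CFB) variables are analysed by ANCOVA without transformation (section 9.5.3.1).

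**The concern.** An area measured against the subject's own baseline need not be positive. A subject who stays at or below the pre-dose glucose has a negative net area, or a zero area if only the part above baseline is counted. The wording of sections 9.5.4 and 9.5.4.1 does not settle which is meant, and the logarithm fails under both.

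The protocol's own procedures foresee falls below baseline. Under section 8.2.3.1, dosing takes place at 45 to <60 mg/dL, with the baseline sample taken about 5 minutes after the insulin infusion stops. Rescue is then provided for: "If plasma glucose is <45 mg/dL (2.5 mmol/L) between t=8 and t=44 minutes". A value that triggers this rule lies below every permitted baseline.

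Such subjects should be mainly on placebo. Section 2.1.3.1 reports that in phase 2 all subjects at all dose levels rose by at least 20 mg/dL within 30 minutes. Section 9.1 assumes at most 50% recovery by 20 minutes on placebo. Whether a subject can be analysed would then depend on both outcome and arm, and the analysed set would no longer be the FAS.

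**Working it through.** **The plan's own figure.** The protocol gives no figure for AUC0-30min. Its only calculation is the 90% power in section 9.1 for 80% versus 50% recovery, 78 versus 39 subjects, two-sided 5%. With unpooled variance, SE = √(0.8×0.2/78 + 0.5×0.5/39) = 0.092, and power = Φ(0.30/0.092 − 1.96) = 90.3%. Other methods give 91.1% (pooled), 90.7% (arcsine), 91.7% (exact chi-square) and 88.9% (exact Fisher). The 90% is reproduced, and the AUC issue does not touch it.

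**An illustrative non-responder.** Take the protocol's sampling times 0, 4, 6, 8, 10, 12, 15, 17, 20, 25 and 30 minutes, with assumed changes from baseline of 0, −1, −2, −3, −3, −4, −4, −4, −3, −2 and 0 mg/dL. The trapezoids are −2, −3, −5, −6, −7, −12, −8, −10.5, −12.5 and −5, which sum to −71 mg·min/dL. Counting only area above baseline gives 0. Neither has a logarithm.

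**How many could be lost, net-area reading.** The protocol gives no mean or SD for this AUC, so these inputs are assumptions. For a normal placebo AUC, the share at or below zero is Φ(−mean/SD), and the mean of those retained is mean + SD × φ(mean/SD)/Φ(mean/SD).

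| Assumed mean / SD (mg·min/dL) | Share ≤0 | Of 39 placebo subjects | Mean of those retained |
|---|---|---|---|
| 0 / 150 | 50% | 19.5 | 120 |
| 100 / 200 | 31% | 12.0 | 202 |
| 200 / 200 | 16% | 6.2 | 258 |
| 200 / 300 | 25% | 9.8 | 328 |
| 300 / 200 | 7% | 2.6 | 328 |
| 300 / 150 | 2% | 0.9 | 308 |

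For dasiglucagon at an assumed mean of 900 and SD of 350, Φ(−900/350) = 0.5%, or about 0.4 of 78 subjects.

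**Direction.** With dasiglucagon as above and placebo SD 200, simulated arithmetic mean differences were:

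| Placebo mean | All 117 subjects | Only subjects with a logarithm | Reduction |
|---|---|---|---|
| 100 | 800 | 704 | 96/800 = 12% |
| 200 | 701 | 649 | 52/701 = 7% |
| 300 | 601 | 579 | 22/601 = 4% |

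The difference shrinks. The protocol's geometric mean ratio has no all-subjects value to compare with, since it does not exist once one value is non-positive.

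**The case against.** Several objections stand.

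- **Exclusion is not written down.** Section 9.9 opens with subject withdrawal, and a fully sampled subject with a non-positive AUC is neither withdrawn nor missing. Section 9 lets the SAP add detail, and a floor or offset could be set there. So the loss is a consequence of the undefined logarithm under a valid-cases approach, not a stated rule. However, the protocol itself prescribes the transformation, and a logarithmic ratio is sensitive to whatever floor is chosen.
- **The size is assumed, and for one reading only.** If only area above baseline counts, a subject is lost only when none of the ten samples from 4 to 30 minutes exceeds baseline, and the normal formula does not apply. The mean-zero case also sits poorly with the planning figure: a linear rise of 20 mg/dL by 20 minutes gives 30²/2 = 450 mg·min/dL by 30 minutes. But 50% recovery is the protocol's upper assumption for placebo, so low responses cannot be ruled out.
- **The secondary objective is dasiglucagon versus GlucaGen.** Non-positive areas are unlikely in either active arm. That contrast is exposed mainly through the shared residual variance, which very small positive placebo areas can inflate on the log scale.

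Three stronger readings are tempting but not supported. A reader might infer that dropping poor placebo responders flatters dasiglucagon; on the mean scale it does the opposite. A reader might infer that rescue glucose seriously inflates the area, because AUC0-30min has no rescue rule while CFB is carried forward from rescue. Yet the rescue rule that applies from 8 minutes holds glucose at 45 to 55 mg/dL. If that target is kept, it adds at most 10 mg/dL × 22 min = 220 mg·min/dL at a baseline of 45, and nothing at a baseline of 55 or above. Only rescue for severe symptoms could add more. Finally, the synopsis might be read as contradicting section 9.5.4.1, but an analogous analysis can mean the same ANCOVA structure, so that conflict is weak.

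**Conclusion.** The point holds in a limited form. The analysis in section 9.5.4.1 cannot be run on every FAS subject if any subject's glucose fails to rise above baseline, and the protocol's own procedures make this likely enough to need a rule. This does not depend on the assumed means and SDs. The number affected does: about 2% to 50% of placebo subjects (roughly 1 to 20 of 39) over the assumed range under the net-area reading, with no estimate available for the other reading. Where subjects are lost, the arithmetic mean difference was 4% to 12% too small in the scenarios simulated.

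A reader might infer that the trial's main result is at risk. It is not: AUC0-30min is listed under other secondary endpoints (section 3.5) and is absent from the testing hierarchy in section 9.5.1. The primary analysis, key secondary endpoints, type 1 error and power are unchanged. This should be corrected, but it does not carry the highest priority.

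**What to change.** In section 9.5.4.1, define AUC0-30min as net baseline-adjusted area, with area below baseline counted as negative. Analyse it untransformed by ANCOVA with treatment and baseline plasma glucose, the same model as for CFB. Report least squares mean differences in mg·min/dL with 95% confidence intervals. Keep the log scale for the PK AUC and Cmax only (section 9.5.5.1). Injection site need not be added, since the CFB model does not contain it.

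As a secondary step, add a sensitivity analysis that applies the existing CFB convention, change at rescue carried forward, to the profile up to 30 minutes.

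The cost is a wording change in the protocol or SAP before unmasking, with no new data. The price in reporting is that the result is a difference rather than a ratio.

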9.5.5 Exposure (PK) endpoints

- Plasma dasiglucagon and GlucaGen concentrations from time zero to 90 minutes: $AUC_{0-90min}$, C_{max} , and t_{max} .

9.5.5.1 Analysis of exposure (PK) endpoints

AUC will be derived as the area under the individual plasma dasiglucagon/GlucaGen concentration profile for PK from 0 to 90 minutes or last valid measurement if this measurement is assessed sufficiently close to 90 minutes (decision to be taken at the masked data review meeting). The standard trapezoidal method will be used, based on actual rather than nominal timepoints.

C_{max} will be determined as the maximum of all valid plasma dasiglucagon/GlucaGen concentrations.

T_{max} will be determined as the timepoint where the maximum of all valid plasma dasiglucagon/GlucaGen concentration measurements for each measurement series is observed.

The log-transformed PK endpoints AUC and C_{max} will be analyzed in the same way as the AUC endpoints.

As t_{max} is a highly discrete endpoint, Wilcoxon's rank sum test for unpaired observations will be used to assess differences between the two treatment groups.

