8.2.3 Visit 2 (dosing visit)

Visit 2 will take place on Day -1 to Day 1.

The subjects will attend the clinical center the day prior to dosing (Day -1) and subject eligibility is rechecked (check of changes between the screening visit and Visit 2) and those subjects eligible to participate should stay onsite overnight. To target a glucose level around 90-110 mg/dL (5.0-6.1 mmol/L) the following morning, subjects may be administered insulin glulisine (Apidra®) at the investigator's discretion either by IV infusion, SC bolus or continuous SC insulin infusion. Dosing will take place the following morning (Day 1).

On Day 1 and prior to the start of the insulin-induced hypoglycemic procedure, those subjects eligible to participate will be randomized to treatment with dasiglucagon, placebo, or GlucaGen.

The following assessments will also take place:

- Document all changes in concomitant medication (prior to the start of the insulin-induced hypoglycemic procedure)
- Check of withdrawal criteria (prior to the start of the insulin-induced hypoglycemic procedure)
- Check of dosing day exclusion criteria (prior to the start of the insulin-induced hypoglycemic procedure)
- Vital signs (prior to the start [within 30 minutes] of the insulin-induced hypoglycemic procedure, and at 30, 90 and 300 minutes after dosing). 12-lead ECG (prior to the start [within 30 minutes] of the insulin-induced hypoglycemic procedure, and at 20, 35, 45, 60, and 300 minutes after dosing)
- Local tolerability (at 30, 120, and 300 minutes after dosing)
- AEs
- Biochemistry, hematology, coagulation (prior to the start of the insulin-induced hypoglycemic procedure [within 30 minutes], and at 30 and 300 minutes after dosing)
- Urine stick pregnancy test (women of childbearing potential only; prior to the start of the insulin-induced hypoglycemic procedure)
- Urinalysis (prior to the start of the insulin-induced hypoglycemic procedure [within 120 minutes])
- Urine drug screen (prior to the start of the insulin-induced hypoglycemic procedure)
- Alcohol breath test (prior to the start of the insulin-induced hypoglycemic procedure)

- Dasiglucagon/GlucaGen plasma concentrations:
 - Pre-dose, 15, 30, 35, 40, 50, 60, 90, and 120 minutes after dosing. The actual time of blood sampling for exposure should not deviate from the nominal time by more than ± 1 minute. Pre-dose is defined as within 2 minutes prior to dosing.
- Plasma glucose concentrations:

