2.1.1 Hypoglycemia

Hypoglycemia in patients with diabetes is defined as episodes of an abnormally low plasma glucose concentration (3). This is a common, unpredictable, and potentially dangerous side effect of treatment of diabetes mellitus, especially with insulin or sulfonylureas. It is more frequent in patients with profound endogenous insulin deficiency, such as occurs in type 1 diabetes mellitus (T1DM) and advanced type 2 diabetes mellitus (T2DM). Treatment of T2DM with insulin causes hypoglycemia progressively and more frequently over time, whereas in T1DM, hypoglycemia is experienced throughout the course of established disease (4).

Symptoms and signs of hypoglycemia are not specific. Patients undergoing a hypoglycemic episode experience unpleasant symptoms such as anxiety, sweating, hunger, tremors, palpitations, paresthesia, nausea and pallor. Depending on its severity, the hypoglycemia may lead to mild confusion, behavioral changes, loss of consciousness, seizures, coma, and death (5).

The incidence of hypoglycemic events or even the fear of hypoglycemia influences patients' adherence to prescribed treatment regimens for diabetes mellitus (6). This leads to inadequate glycemic control, which in turn may lead to an increased risk of diabetic complications (5). Serious clinically significant hypoglycemia is now defined as plasma glucose <54 mg/dL (3.0 mmol/L), while the plasma glucose alert value is defined as <70 mg/dL (3.9 mmol/L) (7). When plasma glucose falls below these values, some kind of treatment strategy is needed.

2.1.2 *Glucagon*

Glucagon is a naturally occurring hormone, secreted from the alpha cells of the pancreatic islets. Glucagon plays a central role in the regulation of glucose homeostasis and is the counterpart of insulin for controlling blood glucose levels (i.e. it acts in opposition to insulin in terms of effects on blood glucose levels) (8,9). Glucagon stimulates hepatic glycogenolysis and gluconeogenesis in hypoglycemic states, thereby restoring glucose homeostasis. Glucagon receptor agonism has also been shown to exert effects on lipid metabolism, energy balance, body adipose tissue mass and food intake (10). Insulin decreases blood glucose levels and cases of hypoglycemia can be reversed by glucagon. Therefore, glucagon is indicated for the treatment of severe hypoglycemia.

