5 TRIAL POPULATION

5.1 Rationale for trial population

Dasiglucagon is in development for the treatment of severe hypoglycemia in insulin-dependent patients with diabetes mellitus. In the present trial, subjects with T1DM are included in the evaluation of efficacy and safety of dasiglucagon under hypoglycemic conditions as this is part of the intended target population. Subjects with T1DM are selected to avoid the endogenous glucagon counter-regulatory response to insulin-induced hypoglycemia that is present in patients with T2DM. The inclusion and exclusion criteria are set to include a trial population that represents the general population of subjects with T1DM.

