6 TRIAL DRUG

6.1 Identity

The following trial drugs will be administered:

- Dasiglucagon, liquid formulation, 1 mg/mL, 0.6 mL delivered in a prefilled syringe.
- Placebo, liquid formulation, 0.6 mL delivered in a prefilled syringe.
- Recombinant glucagon hydrochloride, 1 mg for reconstitution (GlucaGen®, Novo Nordisk) in 1 mL sterile water.

The description of the three trial drugs is provided in Table 1. Dasiglucagon is a stable peptide analog of human glucagon in a ready-to-use liquid formulation for treatment of severe hypoglycemia in insulin-dependent patients with diabetes mellitus. GlucaGen is approved in the EU and US and is indicated for treatment of severe hypoglycemic reactions, which may occur in the management of insulin-treated children and adults with diabetes mellitus.

Table 1 Description of trial drugs

	Test product	Placebo Product	Comparator product
Name	Dasiglucagon	Placebo	GlucaGen®
Active substance	Dasiglucagon	N/A	Recombinant glucagon hydrochloride
Formulation	Liquid formulation, 0.6 mL	Liquid formulation, 0.6 mL	Powder and solvent for reconstitution as 1 mL solution for injection
Strength	1 mg/mL	N/A	1 mg
Device	Single use pre-filled syringe	Single use pre-filled syringe	Powder and solvent for reconstitution packed together in a plastic box. A “hypo-kit”.
Manufacturer	Zealand Pharma A/S, Glostrup (Copenhagen), Denmark	Zealand Pharma A/S, Glostrup (Copenhagen), Denmark	Novo Nordisk A/S, Bagsværd, Denmark

	Test product	Placebo Product	Comparator product
Storage requirements	Store between 2 and 8°C	Store between 2 and 8°C	Store between 2 and 8°C

The quantities of ingredients for dasiglucagon and placebo are provided in Table 2.

Table 2 Quantities of ingredients in dasiglucagon and placebo injection

Component	Amount per mL (dasiglucagon)	Amount per mL (placebo)	Function
Dasiglucagon*	1.0 mg	N/A	
Sodium chloride	10.23 mg	10.23 mg	
Trometamol/Tromethamine	6.06 mg	6.06 mg	
Water for injection	To make 1 mL	To make 1 mL	
Sodium hydroxide	q.s.	q.s.	
Hydrochloric acid	q.s.	q.s.	

*The quantity of drug substance to be used is calculated according to net peptide content and purity.
q.s. = quantum sufficit (quantity required).

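### GlucaGen AUC0-90 and Cmax are taken from raw concentrations with no pre-dose correction, although glucagon is endogenous and a pre-dose PK sample is already drawn

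*Protocol*

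**What the plan says.** Section 9.5.5.1 sets one rule for both drugs. For AUC: "AUC will be derived as the area under the individual plasma dasiglucagon/GlucaGen concentration profile for PK from 0 to 90 minutes". The method is also fixed: "The standard trapezoidal method will be used, based on actual rather than nominal timepoints". For the peak, the rule is that Cmax "will be determined as the maximum of all valid plasma dasiglucagon/GlucaGen concentrations". There is no baseline term in either definition, and the wording is the same in every protocol version in the file. Log AUC and log Cmax then go into the ANCOVA of Section 9.5.4.1, which yields a ratio of geometric means with a 95% CI.

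Other sections bear on this rule:

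- Section 2.1.2: "Glucagon is a naturally occurring hormone, secreted from the alpha cells of the pancreatic islets".
- Section 6.1, on the GlucaGen product: "Recombinant glucagon hydrochloride, 1 mg for reconstitution".
- Section 8.2.3, on PK sampling: "Pre-dose, 15, 30, 35, 40, 50, 60, 90, and 120 minutes after dosing". Pre-dose means within 2 minutes before dosing, and Section 8.2.3.1 treats this sample as a baseline sample.
- Section 9.5.4.1, on glucose: "The AUC will be calculated as the baseline-adjusted area under the plasma glucose profile over time". Section 9.6 likewise takes the insulin AUC above baseline.
- Section 3.5 names the PK endpoints as drug exposure: area under the drug concentration curve, and maximum drug concentration.

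**The concern.** An endpoint called drug exposure should measure what was injected. For dasiglucagon, an analog with 7 substituted amino acids, no endogenous counterpart is expected. For GlucaGen, the injected molecule is the hormone itself. An assay that measures it may also measure what the subject had in plasma before the injection. Any such background enters only the GlucaGen side, because Section 6.6 matches each product to its own assay. The ratio would then be pulled down in one direction.

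The protocol adjusts its other two AUCs, glucose and insulin, for baseline. The PK AUC is the exception, although the sample needed for the adjustment exists. This is a stated rule that fits its endpoint poorly, and a SAP that followed it literally would produce uncorrected values.

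**Working it through.** The protocol states no figure that depends on this rule, so there is nothing to reproduce first. The check asks how far a background would move the results.

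**Inputs from the protocol.** GlucaGen median tmax is 20 minutes (Section 2.1.3.1). PK samples up to 90 minutes fall at 0, 15, 30, 35, 40, 50, 60 and 90 minutes. The AUC uses linear trapezoids over 0-90 minutes.

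**Assumptions.** The GlucaGen curve is one-compartment with first-order absorption. Its half-life is 15 to 45 minutes; the protocol gives a half-life only for dasiglucagon (28 minutes). Native glucagon stays constant at b times the drug Cmax for 90 minutes, with b from 0.5% to 5%. The GlucaGen assay reads native glucagon and the dasiglucagon assay does not. The documents supply none of these.

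**Formulas.** Trapezoids over a constant b × Cmax from 0 to 90 minutes give exactly 90 × b × Cmax, wherever the samples lie. So

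- relative AUC inflation = 90 × b / (AUC0-90 / Cmax);
- factor on the dasiglucagon/GlucaGen AUC ratio = 1 / (1 + inflation).

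**AUC0-90 / Cmax at the protocol's sampling times.** 49.0 min (half-life 15), 50.5 (20), 54.0 (28), 60.2 (45).

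**Example.** Half-life 28 minutes, b = 1%: 90 × 0.01 / 54.0 = 1.67%; factor = 1 / 1.0167 = 0.984.

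**Range over the four half-lives.**

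| Pre-dose level, % of Cmax (assumed) | AUC0-90 inflation | Factor on AUC ratio | Cmax inflation |
|---|---|---|---|
| 0.5 | 0.75-0.92% | 0.991-0.993 | about 0.5% |
| 1 | 1.5-1.8% | 0.982-0.985 | about 1% |
| 2 | 3.0-3.7% | 0.965-0.971 | about 2% |
| 5 | 7.5-9.2% | 0.916-0.930 | about 5% |

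AUC is affected more than Cmax because the background accumulates over the full 90 minutes, while the drug's area equals only about 49-60 minutes at peak level. A continuous curve with half-lives of 8-26 minutes gives AUC0-90 / Cmax of 51-56 minutes, or about 1.6-1.8% per 1%, so the result depends little on the model.

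**The case against.** **The premise is not documented.** The protocol gives no selectivity or quantification limit for the GlucaGen PK assay, no native glucagon level and no GlucaGen concentration. If pre-dose values are below quantification, the correction changes nothing. Section 5.1 points toward a low background: "Subjects with T1DM are selected to avoid the endogenous glucagon counter-regulatory response". This stands, so the point has to be conditional.

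**It is SAP detail.** Section 9 lets the SAP add or refine analysis details, and a baseline rule could go there. In part this stands. But Section 9.5.5.1 does more than stay silent: it prescribes the area under the measured profile and the raw maximum. It does refer PK analysis to the method used for the AUC endpoints, but in a sentence about log-transformed values. That points to the ANCOVA and does not clearly import the glucose baseline adjustment.

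**Sparse sampling acts the other way.** No PK sample falls between 15 and 30 minutes, which brackets the GlucaGen tmax. With half-lives of 8-26 minutes, the planned samples read AUC0-90 about 4.1-4.3% low and Cmax about 3.3-3.7% low. For a background up to 2% of Cmax, that exceeds the inflation. The figures are right, so the net error of the uncorrected AUC may even be negative. But this is a separate error, and one does not validly correct the other. Here, overstated means relative to what the same samples would show without native glucagon.

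**The correction is imperfect.** One pre-dose value, taken in hypoglycemia, need not hold for 90 minutes of rising glucose. Its measurement error enters every later difference, and setting negatives to zero biases slightly upward. This stands and is the reason to show both versions.

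**No decision depends on it.** Correct: PK is outside the testing hierarchy, and the synopsis makes comparisons with GlucaGen descriptive.

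**Conclusion.** The point holds as a conditional, low-impact improvement. To the extent that the GlucaGen assay reads native glucagon above its quantification limit, the rule in Section 9.5.5.1 overstates GlucaGen exposure and understates the dasiglucagon/GlucaGen ratio. Under a constant background this amounts to about 1.5-1.8% of AUC0-90 and about 1% of Cmax for each 1% that the pre-dose level represents of Cmax. At 2% of Cmax or less, the AUC effect stays under 4%.

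A reader might infer that the exposure ratio is biased as a matter of fact, or materially so. The documents do not support that, because they give neither the native level nor the assay's selectivity. Nor does anything here touch the efficacy conclusions: the primary and key secondary tests compare glucose outcomes between dasiglucagon and placebo. The PK ratio compares two molecules at different doses (0.6 mg and 1 mg) and carries no equivalence margin.

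**What to change.** In Section 9.5.5.1, report GlucaGen AUC0-90 and Cmax in two versions: as measured, and from concentrations minus the subject's own pre-dose value. Take pre-dose values below quantification as zero and set negative differences to zero. Leave dasiglucagon unchanged, provided its assay does not read native glucagon, and say so. If the GlucaGen assay does not read native glucagon, a statement to that effect makes the correction unnecessary.

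The cost is a sentence or two in the plan and one additional set of derived values. The pre-dose sample is already scheduled for every subject. The choice should be fixed before unmasking so that it is not made after the ratios are seen.
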